4.5. Withdrawal of Patients

Patients will be informed that they have the right to withdraw their consent to participate in the study at any time for any reason, without prejudice to their medical care. The Investigator also has the right to withdraw patients from the study, after discussion with the Sponsor, for any of the following reasons:

- Non-adherence to study drug regimen or protocol requirements.
- Non-compliance with instructions or failure to return for follow-up.

If a patient is withdrawn or discontinued from the study, the primary reason for withdrawal from the study is to be recorded in the source documents/electronic case report form (eCRF).

Any patient that discontinues treatment prior to completing the study should be strongly encouraged to complete all remaining visits and procedures as outlined in the Schedule of Assessments (SOA) in Section 6, even if they are no longer receiving study drug.

In case of discontinuation, all AEs should be followed as described in Section 7.4; any skin AEs should continue to be followed, if at all feasible, for ~60-90 days to confirm near or complete resolution (as has been shown in previous studies).

The Sponsor will provide support for patient and caregiver travel, will make available visiting home health care professionals, and any other necessary logistical support to ease the burden on the patient to facilitate compliance.

4.6. Duration of Patient Participation

Individual patient participation in this study is expected to last for approximately 69 weeks (~3 week screening period plus 66 weeks of treatment across Periods 1 through 3).

The end of the trial will be defined as the last patient's last visit.

5. STUDY TREATMENTS

5.1. Study Drugs

All study drugs are for investigational use only and are to be used only within the context of this protocol. All investigational study drugs (setmelanotide and placebo) will be supplied by the Sponsor.

Setmelanotide is the investigational test drug being evaluated in this clinical study. Setmelanotide is an 8 amino acid, cyclic peptide that is highly selective and potent agonist at the human MC4R.

Setmelanotide drug product (setmelanotide mPEG-DSPE formulation) is a sterile solution for injection. The product is manufactured at a concentration of 10.0 mg/mL.

The reference therapy for the double-blind period of this study is a placebo vehicle.

Setmelanotide and placebo are clear, colorless to slightly opalescent solutions essentially free of visible particulates, and are suitable for a double-blind study.

5.2. Study Drug Administration and Dose Escalation

5.2.1. Administration

Study patients will receive study drug by SC injection QD (administered in the morning).

There will be extensive training of patients in drug administration including educational materials. Study specific training materials will be provided to both the investigative staff and study participants and caregivers. The Sponsor will provide extra placebo supplies for use during training.

The goal is for the patient or their caretaker to successfully self-administer the study drug at home. Given the rarity of BBS and AS, arrangements may be made for those who are not able to successfully self-administer the study drug to have assistance by a visiting home health care practitioner.

Patients and/or their caretakers (including home health practitioners) will be responsible for all procedures associated with study drug administration, ie, drawing up and self-administering the study drug QD (including during the practice sessions).

To ensure patients or their caregivers can successfully self-administer study drug, a training session(s) in the clinic with placebo (or saline) will occur during screening before entering the randomized, double-blind study period. This training/practice can occur as many times as necessary throughout the study to assure proper technique. The training/practice does not pertain to the home health practitioners.

Patients will be required to fast overnight for all clinic visits. Water will be allowed throughout the fasting period.

5.2.2. Study Drug Dose Escalation and Adjustments

Dose escalation will occur during the first 2 weeks of both the double-blind placebo-controlled and the open-label study periods (see Table 1). The reason for repeating the dose escalation

procedure at the start of the open-label period is to maintain the blind of the study and not reveal which group originally started with placebo/active treatment.

Doses should not be adjusted after the dose escalation phase has been completed unless discussed and approved by the Sponsor.

Table 1 Dose Escalation Schedule

Study Week	Patients ≥16 years of age (Dose in mg)	Patients <16 years of age Dose (mg)
1	2.0 or placebo	1.0 or placebo
2	2.0 or placebo	2.0 or placebo
3-14	3.0 or placebo	3.0 or placebo
15	2.0	1.0
16	2.0	2.0
17-78	3.0	3.0

5.3. Method of Assigning Patients to Treatment

Patients who qualify for the study will return to the site on Day 1 of the double-blind period. Prior to randomization, the Investigator will ensure that the patient continues to meet inclusion and exclusion criteria. Patients who continue to be eligible to participate in the study will be assigned a unique randomization number based on a randomization code that will be generated prior to the start of the study. The randomization number codes the patient's initial treatment assignment (for the double-blind period) to either setmelanotide or placebo. The randomization scheme will randomize patients in a 1:1 ratio, stratified by age group (≥12 years or <12 years) and disease (BBS or AS), to receive either setmelanotide or placebo during the first 14 weeks of the study. Randomization numbers will not be re-used once assigned.

5.4. Blinding, Packaging, and Labeling

5.4.1. Blinding and Breaking the Blind

This study will be open label, with the exception of a 14-week double-blind, placebo-controlled period.

The Investigator, study site staff, clinical research organization staff providing site management, and Medical Monitor will not have access to the actual treatment assignment administered during the 14-week double-blind, placebo-controlled treatment period (Period 1), except in the case of an emergency. Every attempt will be made to maintain the blind through the end of the 38-week, open-label treatment period (Period 2) (ie, until the database snapshot prior to completing the primary statistical analysis). Breaking the blind for a patient should be done only in the event of a medical emergency where the identity of study drug is necessary to appropriately treat the patient. The request to break the blind should be discussed with the Medical Monitor and the Sponsor, whenever possible. If the blind is broken, the reason, when and how the blind was broken will be documented.

5.4.2. Packaging and Labeling

All study drugs, including placebo or saline for practice, will be supplied by the Sponsor; placebo/saline for practice SC administration will not be blinded.

Packaging and labeling will be prepared to meet all regulatory requirements.

To ensure that the patient and site are blinded with respect to each patient's randomized treatment assignment, placebo and setmelanotide are identical in appearance and are supplied in identical packaging. Each vial will contain a code that identifies the contents as either placebo setmelanotide. At each site visit during the double-blind period, an unblinded study pharmacist will select the correct study drug based on the patient's randomized treatment assignment and will provide the blinded study medication to the patient or the patient's caregiver.

Following completion of the double-blind period, the study pharmacist will provide open-label (ie, unblinded) vials of setmelanotide to the patient or the patient's caregiver.

5.5. Preparation, Handling, and Storage

All study drug must be kept in a secure, limited-access storage area at a temperature between 2°C to 8°C. Both setmelanotide and placebo are stable at room temperature for a short period that will allow patients to transport study drug home; ice packs and cooler bags will be provided for patients and caretakers who will travel long distances from the clinic. Patients will be encouraged to proceed directly home after clinic visits in which study drug is dispensed to minimize the amount of time the study drug is exposed to elevated temperatures.

A separate pharmacy manual with specific instructions will be provided to the investigative site.

5.6. Assessment of Treatment Compliance

To evaluate the efficacy, of the study drug, it is critical that patients receive study drug as directed. All used study drug will also be collected to assess compliance with the protocol.

Patients and/or caretakers will be required to maintain a study drug diary to monitor compliance. In addition, the time of dosing will be recorded in the patient diary. This information will be recorded directly into an electronic data capture device. Home nurses will be available, as needed, for additional training and to reinforce compliance.

If a patient does not receive the entire dose of study drug, the amount administered will be recorded. In addition, the reason(s) is to be recorded in source documents and the eCRF.

Additionally, at all clinic visits, a blood sample will be collected prior to dosing in clinic to measure trough concentrations of setmelanotide in plasma.

5.7. Study Drug Accountability

Accountability for the study drug at the study site is the responsibility of the Investigator. The Investigator will ensure that the study drug is used only in accordance with this protocol. Where allowed, the Investigator may choose to assign drug accountability responsibilities to a pharmacist or another appropriate individual. Drug accountability records indicating the delivery date to the site, inventory at the site, use by each patient, return of all used study drug to the study center, and return to the Sponsor (or disposal of the drug, if approved by the Sponsor) will

be maintained by the clinical site. These records will adequately document that the patients were provided the medication (setmelanotide or placebo) and doses as specified in the randomization code and protocol and should reconcile all study drug received from the Sponsor. Reasons for departure from the expected dispensing regimen must also be recorded. Accountability records will include dates, quantities, batch/serial numbers, expiration dates (if applicable), and patient numbers. The Sponsor or its designee will review drug accountability at the site during monitoring visits.

All unused and used study drug will be returned by patients, and retained at the site until inventoried by the monitor. All unused, used or expired study drug will be returned to the Sponsor or if authorized, disposed of at the study site and documented.

5.8. Prior and Concomitant Treatment

5.8.1. Permitted Medication

Female patients may use hormonal contraception as well as hormone replacement therapy.

Unless concomitant medications are likely to present a strong potential safety concern, the general goal of this protocol is to allow as many as possible patients with these ultra-rare conditions to participate in the study. Therefore, patients are allowed chronic concomitant medications (eg, as described below) while participating in the study:

- Growth hormone
- Contraceptives (see Section 6.2.1 for requirements for contraception)
- Hormone replacement therapy (eg, estrogen, progestins, androgens)
- Anti-hypertensives
- Statins and other lipid-lowering therapies
- Thyroxine or other thyroid supplements
- Other medications commonly used in obese patients including: endocrine therapies (eg, estrogens, bisphosphonates, hydrocortisone, vitamin and calcium supplements, diabetic therapies including insulin); and other medications (eg, carnitol, Coenzyme Q10, vitamins, anti-constipation medications, anti-allergic medications).
- Apart from low threshold drugs (eg, anticonvulsants, digoxin, warfarin sodium), other
 medications may be permitted if on a stable dose (for at least 1-2 months) upon
 consultation with the Sponsor.

There is little evidence that setmelanotide will result in drug interactions at present, but data are limited. Patients and caretakers should be carefully questioned about medication use to ensure that potential patients are carefully warned of possible side effects from drug interactions that could occur with the specific list of medications that an individual patient will be receiving.

Patients will be reminded at each visit that if it becomes necessary for a patient to take any other medication during the study, from Screening until the Final Study Visit, they must inform the study staff immediately, and the specific medication(s) and indication(s) must be discussed with the Investigator. All concomitant medications taken during the study must be recorded in the source documents and on the eCRF.

5.8.2. Prohibited Medication and Substances

Medications, including those approved to treat obesity, that could impact the efficacy results of this study are prohibited (eg, orlistat, lorcaserin, phentermine-topiramate, naltrexone-bupropion, liraglutide).

Stimulant (and non-stimulant, if decreased appetite/weight loss is listed side effect) medication (eg, to treat attention deficit hyperactivity disorder [ADHD]) cannot be started during the study. Patients who have been on a stable dose and regimen for at least 2 months prior to study entry may continue to receive the same dose and regimen during the study.

Anorectic agents or drugs with anorexia as a non-rare side effect are prohibited for the duration of the study.

5.8.3. Concomitant Procedures

Concomitant procedures conducted during the study, including those used to treat adverse events, are to be reported on the eCRF.

6. STUDY ASSESSMENTS

6.1. Overview of Schedule of Assessments

The SOA for treatment Periods 1 and 2 is depicted in Table 2 and the SOA for the treatment Period 3 and the early termination visit (if needed) is depicted in Table 3.

Although the study procedures and assessments required per protocol are classified as "No or Minimal Risk" (apart from DXA which is classified as "Minor Increase over Minimal Risk") per the 2008 Guidance Document "Ethical Considerations for Clinical Trials on Medicinal Products Conducted with the Pediatric Population", considerations for reducing pain in distress in participants younger than 18 years of age are included in Appendix 11.7.

Upon providing informed consent, patients will enter the Screening Period. During the Screening Period, patients will be assessed for eligibility and instructed to complete a hunger questionnaire (Appendix 11.5) daily to enhance the understanding of hunger associated with BBS and AS, prior to treatment with study medication. During Screening, a detailed medical history will be obtained, including medical chart review (Appendix 11.3), to collect information pertaining to the natural history of BBS and AS.

After the Screening Period in which confirmation of patient eligibility and ability for patients or their caretakers to successfully self-administer study drug is determined (or if arrangements for a visiting home health care practitioner are necessary), patients will be randomized to receive either setmelanotide or placebo and will enter the 14-week double-blind treatment period (Period 1). Following completion of the double-blind treatment period, all patients will receive setmelanotide in a 38-week open-label treatment period (Period 2) followed by a 14-week open-label treatment period (Period 3).

Any patient withdrawing from the study will complete the Early Termination Visit, if possible, and will be encouraged to complete all remaining study visits. For those patients not willing to complete study visits at the clinic, home health care practitioner visits or telephone follow-up may be acceptable to obtain minimum patient self-reported data (ie, weight, AEs, etc.).

Detailed descriptions of the provided in the following sections.

Patients will be required to fast overnight on the day preceding all site visits, beginning with the initial Screening Visit. Patients will be allowed to take their usual medications with a sip of water on the morning of each clinic visit.

The Screening Period can occur within ~3 weeks of Day 1, and should be scheduled within this timeframe to allow test results to be received and continued eligibility of patients confirmed prior to the first dose on Day 1. Assessments may occur over multiple days during the Screening Period. To obtain sufficient baseline data on symptoms of hunger (collected daily), the screening period should be a minimum of 2 weeks.

To provide flexibility to the patient and study staff, the actual scheduling of clinic visits can occur within a flexible window of time (ideally ± 3 days). However, as these patient populations are ultra-rare, all data collected, even if outside of visit windows, will be included in all analyses of endpoints.

Additionally, if the patient resides a considerable distance from the Investigative Site, arrangements may be made for a home health practitioner to conduct a visit at the patient's home or for the patient to be seen at their local physician's office, to obtain the applicable data/samples. These arrangements must be approved by the Sponsor in advance, to be sure that important data/samples can be properly collected, and any safety procedures robustly implemented.

However, patients must be seen at the Investigative Site at an absolute minimum at least once for Screening, and for visits for Weeks 1, 3, 15, 17, 29, 41, 53, and 66 or Early Termination visit.

			Double-Blind Treatment (Period 1)				38-Week Open-Label Treatment (Period 2)								
	Screening Visit		T or P		SET o	r PBO	SET Escalation			SET					
Visit (V) Number	V1	V2		V3	V4	V5	V6		V7	V8	V9	V10	V11	V12	V13
Study Week	-3	1	2	3	7	11	15	15	17	23	29	35	41	47	53
Study Day	(n/a)	1	8	15	43	71	99	106	113	155	197	239	281	323	365
Informed consent/assent	X														
Inclusion/exclusion review	X	X													
Medical history review	X														
Genetic testing ¹	X														
Archive sample for storage ²		Х					Χţ								Χţ
Comprehensive skin exam ³	X	Х													
Fitzpatrick scale	X	Х													
Pregnancy test ⁴	X	Χ†		Χţ	Χţ	Χţ	Χţ		Χţ						
Study drug administration/dispense ⁵		X		X	X	X	X		Χ	X	X	X	X	X	X
Daily hunger questionnaire8	X	•						— Dai							
Global hunger assessment ⁹	X			Χţ			Χţ		Χţ		Χţ				Χţ

			Double-Blind Treatment (Period 1)				38-Week Open-Label Treatment (Period 2)								
	Screening Visit		SET or PBO Escalation		SET or PBO		SET Escalation			SET					
Visit (V) Number	V1	V2		V3	V4	V5	V6		V7	V8	V9	V10	V11	V12	V13
Study Week	-3	1	2	3	7	11	15	15	17	23	29	35	41	47	53
Study Day	(n/a)	1	8	15	43	71	99	106	113	155	197	239	281	323	365
Injection site inspection ²¹		Χ		X	X	X	X		X	X	X	X	X	X	X
Concomitant medications review	Х	Χ	X	X	X	X	X	X	X	Χ	Χ	X	X	Χ	X
Nutritional counselling and monitoring	Х	Х		Х	Х	Х	Х		Χ	Χ	Х	Х	Х	Х	Х

- † Assessment/sample should be performed/obtained prior to administration of study drug.
- 1 A blood sample will be obtained at Screening to confirm a genetic diagnosis of AS or BBS. However, patients may be entered into the study based on clinical diagnosis of BBS (≤10% of BBS patients) or prior genetic diagnosis of BBS (≥90% of BBS patients) or AS (100% of AS patients) (refer to Section 4.2). This sample may also be used for genotyping other obesity-related genes. The DNA will not be studied or "typed" for any other purpose, unless patients are re-consented.
- 2 Extra retain samples will consist of 2 serum and 2 plasma (K2EDTA) vacutainer tubes and two 5ml urine tubes.
- 3 A comprehensive skin evaluation will be performed by a dermatologist. Any concerning lesions identified during the screening period will be biopsied and results known to be benign prior to first dose of setmelanotide. If the pre-treatment biopsy results are of concern, the patient will be excluded from the study.
- 4 A urine pregnancy test may be performed in order to expedite availability of results prior to dosing on Day 1. All other pregnancy tests will be serum; dosing may continue with results pending.
- 5 Patients/caretakers will draw up and self-administer/administer the drug once daily in the morning beginning the morning of Day 1 and for the duration of dosing. On days with clinic visits, the patients/caretakers will administer the drug in the clinic in the presence of the clinical staff to assure proper technique. Patients/caretakers will return all used vials to the clinic when they visit (the number recorded) and both clinic administered study drug, as well as outpatient study drug administration will be recorded in a study diary.

⁸ Daily hunger questionnaire scores will be recorded on a daily basis, prior to the patient's morning meal. If the patient is unable to assess their own hunger due to impaired cognitive function, a parent/caregiver assessment of hyperphagia will be completed instead (see Appendix 11.5.2).

⁹ Global hunger questions (Appendix 11.5) will be administered in clinic as follows: Question 1 will be asked at Screening, and Questions 1 and 2 will then be asked as specified in the SOA once dosing has been initiated (Day 1).

21	Injection site evaluations and scoring (by the clinical staff) will include identification and measurement of areas of erythema, edema, and induration, as well as the presence of localized pain, tenderness, and itching. Additional evaluation data can be collected at any visit where there are injection site reactions even if not a timepoint for formal assessment.

Table 3 Schedule of Assessments: 14-Week Open-Label Treatment (Period 3) and Early Termination Visit

Visit Number (V) V14 V15 (EOS) Study Week 60 66 Study Day 414 462 Archive sample for storage¹ X† Comprehensive skin exam² X X Fitzpatrick scale X X Pregnancy test³ X† X† Study drug administration/dispense⁴ X X Daily hunger questionnaire² — Daily† — X X† Global hunger assessment⁴ X† X† X† Concomitant medications review X X X Nutritional counselling and monitoring X X X		14-Week Open-l (Peri		
Study Day 414 462 Visit Archive sample for storage¹ X† X Comprehensive skin exam² X X Fitzpatrick scale X X Pregnancy test³ X† X† Study drug administration/dispense⁴ X X Daily hunger questionnaire³ Daily† X Global hunger assessment® X† X† X† X†	Visit Number (V)	V14	V15 (EOS)	
Study Day 414 462 Visit Archive sample for storage¹ X† X Comprehensive skin exam² X X Fitzpatrick scale X X Pregnancy test³ X† X† Study drug administration/dispense⁴ X X Daily hunger questionnaire³ Daily† X Global hunger assessment® X† X† X† X†	Study Week	60	66	Early Termination
Comprehensive skin exam² X		414	462	Visit
Fitzpatrick scale Pregnancy test³ X† X† X† X† X† X† Study drug administration/dispense⁴ X Daily hunger questionnaire³ Global hunger assessment® X† X† X X X Concomitant medications review X X X X X X X X X X X X X X	Archive sample for storage ¹		Χ†	
Pregnancy test³ X† X† X† X† Study drug administration/dispense⁴ X X Daily hunger questionnaire7	Comprehensive skin exam ²		X	X
Study drug administration/dispense⁴ X X X Daily hunger questionnaire ⁷ ← Daily† → X Global hunger assessment [®] X† X† Concomitant medications review X X X X	Fitzpatrick scale		X	X
Daily hunger questionnaire ⁷ Global hunger assessment ⁸ X† X† X† X† Concomitant medications review X	Pregnancy test ³	Χţ	Χţ	Χ†
Global hunger assessment [®] X† X† X† X† Concomitant medications review X X X	Study drug administration/dispense ⁴	X	X	
Global hunger assessment [®] X† X† X† X† Concomitant medications review X X X				
Global hunger assessment ⁸ X† X† Concomitant medications review X X X	Daily hunger questionnaire ⁷	Da Da	ilv÷	Y
Concomitant medications review X X X		- 50		
	Concomitant modications rovious		V	· ·

- † Assessment/sample should be performed/obtained prior to administration of study drug.
- 1 Extra retain samples will consist of 2 serum and 2 plasma (K2EDTA) vacutainer tubes and two 5ml urine tubes.
- 2 A comprehensive skin evaluation will be performed by a dermatologist.
- 3 All pregnancy tests will be serum; dosing may continue with results pending.
- 4 Patients/caretakers will draw up and self-administer/administer the drug once daily in the morning. On days with clinic visits, the patients/caretakers will administer the drug in the clinic in the presence of the clinical staff to assure proper technique. Patients/caretakers will return all used vials to the clinic when they visit (the number recorded) and both clinic administered study drug, as well as outpatient study drug administration will be recorded in a study diary.

- Daily hunger questionnaire scores will be recorded on a daily basis, prior to the patient's morning meal. If the patient is unable to assess their own hunger due to impaired cognitive function, a parent/caregiver assessment of hyperphagia will be completed instead (see Appendix 11.5.2).
- 8 Global hunger Questions 1 and 2 (Appendix 11.5) will be asked.

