6.2. Patient Requirements

6.2.1. Contraception

Setmelanotide has not been completely evaluated in nonclinical Developmental and Reproductive Toxicology Studies to date; therefore, the effects of setmelanotide on embryo-fetal development are unknown at this time. It is imperative all study patients adhere to the contraception requirements as outlined below.

Females must not be pregnant and must have a negative serum pregnancy test result at the Screening Visit and negative urine pregnancy test on Day 1, with results known prior to initiating dosing; pregnancy testing will be monitored during the study.

For female patients who are able to bear children, a highly reliable form of contraception must be used/practiced throughout the study and for 90 following the study. Highly reliable acceptable for of contraception include: hormonal (ie, oral, implantable, or injectable) and single-barrier method (ie, condom), or an Intrauterine Device (IUD) and single-barrier method (ie, condom) or vasectomized partner. True abstinence is acceptable only if it is the preferred and usual lifestyle of the patient.

Females of non-childbearing potential, defined as surgically sterile (status post hysterectomy, bilateral oophorectomy, or bilateral tubal ligation) post-menopausal for at least 12 months (and confirmed with a screening FSH level in the post-menopausal range), or failure to have progressed to Tanner Stage V and/or failure to have achieved menarche, do not require contraception during the study. Younger female patients who are not sexually mature will be assessed for Tanner staging and advised accordingly.

It is not known if this treatment will affect spermatogenesis. Therefore, males with female partners of childbearing potential must agree to use contraception (eg, if they have not had a vasectomy then should either (a) abstain from reproductive sexual intercourse or (b) use a double barrier method (ie, condom and diaphragm and spermicide) if they become sexually active during the study and for 90 days following the study. Male patients must not donate sperm for 90 days following their participation in the study.

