8.3. Definition of Baseline

Baseline for statistical analyses of data from the double-blind period is defined as the last available measurement prior to the randomization (ie, Day 1), for patients randomized into either the setmelanotide or placebo group.

Baseline for statistical analyses following ~52 weeks setmelanotide treatment is defined as follows:

- For patients initially randomized into the setmelanotide group, baseline is defined as the last available measurement prior to the randomization (ie, Day 1)
- For patients initially randomized into the placebo group, baseline is defined as the last available measurement prior to the first dose of open-label setmelanotide treatment (ie, Week 14 or pre-dose Week 15)

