- Example 3: A patient who was initially randomized to placebo in Period 1 but may have been in the study for only 10 months, having received 3 months placebo then 7 months of active setmelanotide. The patient's primary endpoint will be defined as the patients ~12 months active treatment measurement as generated via multiple imputation method described above, since the patients active setmelanotide treatment duration is less than 10 months.
- Example 4: A patient who was initially randomized to placebo in Period 1 but may have been in the study for 14 months, having received 3 months placebo then 11 months of active setmelanotide. The patient's primary endpoint will be defined as the closest done to 52-weeks of active treatment within the 10-14 months window.

There are two planned visits in Period 3 (14-week open-label treatment): Visit 14 (~Week 60) and Visit 15 (EOS, ~Week 66). The analyses and summaries on data collected in this period will not be a main priority of the primary analysis for NDA submission or analyses in other regulatory agencies. However, an additional supportive analysis may be provided on these data after the approximately last patient in pivotal cohort completes the last visit at the end of period 3.

The additional supportive analysis and summary at end of period 3 will be based on relative visits/days (i.e., staggered alignment) from the first dose of the setmelanotide, below examples illustrate the staggered alignment for analysis,

- V2 (Week 1) of patients initially randomized in setmelanotide group (planned first dose visit of setmelanotide) will align with V6 (Week 15) of patients initially randomized in placebo group (i.e, planned first dose visit of setmelanotide).
- V13 (Week 53) of patients initially randomized in setmelanotide group (~52 week visit on setmelanotide) will align with V15 (Week 66) of patients initially randomized in placebo group (i.e, ~52 weeks visit on setmelanotide).
- Other visits will be aligned in a similar fashion.

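### Placebo-first patients can take their first setmelanotide dose at V6 (Week 15) before that visit's pregnancy result is known

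*Protocol*

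**What the plan says.** Protocol Section 6.2.1 states that "the effects of setmelanotide on embryo-fetal development are unknown at this time". It requires a negative serum test at Screening and a "negative urine pregnancy test on Day 1, with results known prior to initiating dosing". After that it says only that pregnancy testing is monitored. It also requires that "a highly reliable form of contraception must be used/practiced throughout the study" by patients able to bear children.

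Protocol Table 2 schedules a pregnancy test at V6 with a dagger, which means: "Assessment/sample should be performed/obtained prior to administration of study drug". The dagger governs when the sample is taken, not when the result must be available. Footnote 4 allows a urine test so that the Day 1 result is back in time, and then adds: "All other pregnancy tests will be serum; dosing may continue with results pending". SAP Table 1 carries the same footnote.

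Protocol Section 8.3 sets the 52-week baseline of the placebo group at the last measurement "prior to the first dose of open-label setmelanotide treatment (ie, Week 14 or pre-dose Week 15". SAP Sections 2.1 and 3.11.1 likewise place that group's first active dose at Week 15 (V6).

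**The concern.** The reason given for the known-result rule is the unknown effect of setmelanotide on the fetus. For patients who start on setmelanotide, the Day 1 rule applies at first active exposure. For patients who start on placebo, it applies 14 weeks too early for that purpose. When they do reach setmelanotide, the text expressly lets the dose go ahead while the result is awaited.

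If contraception fails and the pregnancy is not detected at V5, such a patient can begin setmelanotide while pregnant and continue until the V6 serum result returns. This is a matter of patient safety. It has no bearing on power, type I error or the validity of the efficacy analyses.

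**Working it through.** The plan gives no figure of its own here, so the check is a reading of the rules followed by date and dose arithmetic.

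**Which rule applies at V6**

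| Test | Result must be known before dosing? | Source |
|---|---|---|
| Screening (serum) | Yes | Protocol 6.2.1 |
| Day 1 (urine) | Yes | Protocol 6.2.1 |
| V6 (serum, sampled before the dose) | No | Table 2 footnote 4 and dagger note |

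Inclusion criterion 5 also requires confirmed non-pregnancy, but Table 2 marks the eligibility review only at Screening and V2. Nothing in the text available sets a separate rule for V6.

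**Timing** (study days from Protocol Table 2)
- Tests before V6: Screening, Day 1, V3 (Day 15), V4 (Day 43), V5 (Day 71), so 5 tests.
- Last test before V6: 99 − 71 = 28 days earlier. With the ±3-day window at both visits, 28 − 6 = 22 to 28 + 6 = 34 days. The window is described as ideal, so these are not hard limits.
- Last test whose result had to be known before a dose: 99 − 1 = 98 days earlier.

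**Patients**
- The documents give no count of females of childbearing potential. The lower bound is 0.
- With 1:1 allocation the upper bound is 30 × 1/2 = 15 of the planned patients, or 38 × 1/2 = 19 of the pivotal cohort. Both include males and females not of childbearing potential. The supplemental cohort is not counted, because its size is not given.

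**Exposure before the V6 result**
- Serum turnaround is not stated. Assume T = 0 to 7 days, with one dose a day. Week 15 doses are from Protocol Table 1.
- Age 16 or over: 2 mg × T = 0 to 14 mg.
- Under 16: 1 mg × T = 0 to 7 mg.

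**Comparison with what the plan already accepts**
- The longest scheduled interval between tests is V13 (Day 365; test marked in SAP Table 1) to V14 (Day 414; Protocol Table 3): 414 − 365 = 49 days. At 3 mg a day, 49 × 3 = 147 mg.
- The assumed worst case at V6 is 14/147, or about one tenth of that.

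**The case against.** The best defence is that the plan is coherent. It requires a known negative result at entry and then monitors, and footnote 4 carries that out. This stands. A reader might infer that Section 6.2.1 and footnote 4 contradict each other. They do not, because the known-result rule names Screening and Day 1, and the footnote covers the later tests.

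A reader might also infer that placebo-first patients are less well protected overall. The documents do not support this. If conception follows a negative V5 test, a setmelanotide-first patient can take up to 28 doses of 3 mg (84 mg) before the V6 sample is even drawn. A placebo-first patient has taken none. What remains is narrower: exposure between visits cannot be avoided by a test, whereas at V6 the patient is on site, has been sampled and has not yet been dosed.

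Table 2 footnote 3, which wants biopsy "results known to be benign prior to first dose of setmelanotide", may look like a precedent for tying safety results to first active dose. It is not one. It concerns lesions found during screening, exclusion criterion 10 requires the result before enrolment, and Table 2 shows no repeat skin examination at V6. That check, too, is made at entry.

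Three further limits stand:
- SAP Section 4.7 expected every pivotal patient to have finished Period 1 by about the end of the first quarter of 2020, and the SAP is dated 29 October 2020. On that timeline a change now would help only patients who have not yet reached V6, such as any in the supplemental cohort. Their number is not stated.
- A urine test may miss a very recent conception. The documents give nothing from which to judge how often.
- Protocol Section 7 and the protocol version of 26 August 2020, on which the SAP is based, are not available here. Either could contain a further rule, although the SAP still repeats footnote 4.

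**Conclusion.** The point holds as a low-probability gap at first active exposure. The text lets placebo-first females of childbearing potential receive their first setmelanotide dose before that visit's pregnancy result is known, with the previous test nominally 28 days old. Harm would require a failure of mandatory contraception and a pregnancy not detected at V5.

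The size is small: at most about 15 of 30 planned or 19 of 38 pivotal patients, and in practice fewer. The 14 mg upper figure for exposure rests on the assumed 7-day turnaround. The case for change rests on how little it costs to close the gap at first exposure, not on a large dose or a large number of patients. It is a cheap improvement rather than the correction of an error.

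**What to change.** Amend Protocol Table 2 footnote 4 and Section 6.2.1 so that:
- on Day 1 and at V6 (Week 15), every female of childbearing potential has a negative urine pregnancy result in hand before the dose;
- if the V6 urine test is positive, the dose is held until the serum result is known;
- the V6 serum sample is kept;
- at all other visits after Day 1, dosing may go ahead while serum results are awaited, as now.

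Apply the V6 check in both arms, so that it reveals nothing about the Period 1 assignment, which Protocol Section 5.4.1 aims to keep blinded through Period 2. The matching footnote in SAP Table 1 needs only a conforming edit, since the SAP does not govern dosing.

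The cost is one rapid urine test per eligible patient and a short wait. No visit is added: Week 15 is already a mandatory site visit with in-clinic dosing and a pre-dose pregnancy sample. Urine is already collected there for the archive, and Day 1 already uses a urine test for this purpose. The change benefits any patient who has not yet reached V6.
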